STUDY PROTOCOL WITH SAP

TITLE

Therapeutic exercise protocol for the prevention of anterior cruciate ligament injuries in female football players with dynamic knee valgus.

DOCUMENT DATE: 30/07/2023

INTRODUCTION

In recent years there has been an exponential growth of women participating in team sports such as football. Around 29 million footballers worldwide are women. In addition, the numbers are constantly growing with an estimated 51% increase in the number of registered players, as is the interest of the female society in this sport¹. The popularity and visibility of women's football is associated with an increase in the number of lower extremity injuries, especially with a high risk of knee injuries. Of all the knee injuries that can occur, women are particularly susceptible to anterior cruciate ligament (ACL) injuries. The ACL plays an important role in knee kinematics². It stabilizes the joint in full extension, prevents rotational loads and anterior displacement of the tibia³. These injuries are a major current problem^{4,5} accounting for 16% to 32% of all injuries and 43% of the injury burden during the sports season⁶. Regardless of their level of participation, female footballers have between 2 and 8 times⁷ times the risk of suffering ACL injuries compared to their male counterparts⁵ performing similar training^{8,9,10}. Injury incidence rates among female soccer players range from 1.1 to 3.1 injuries per 1000 hours of training and from 12.6 to 23.6 injuries per 1000 hours of play over the past decade¹.

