Current training methods include preventive strategies focused on modifying neuromuscular and biomechanical risk factors^{31,32} using non-football-specific tasks such as eccentric exercises or verbal or visual *feedback* combined with plyometric, *core*, balance, resistance or trunk strengthening exercises. These could be the most effective to positively modify the screening, identification and correction of dangerous movement patterns^{1,26} such as DKV during jump-landing tasks^{14,21,31,33,34}. However, no uniform criteria have been established to design a precise intervention protocol, with specific tasks linked to women's football, nor has it been proposed to optimize current programs despite having a high number of injuries associated with DKV^{33,34}. On the other hand, there is no consensus or unification on the establishment of defined parameters regarding the effective dosage of a specific training program, since there is great heterogeneity in terms of the doses and times of the scheduled exercises. These preventive programs are effective in the short term, but it is not equally confirmed whether they produce positive effects in the long term³¹. Current evidence reports that the implementation of specific preventive programs according to the sport practiced is imperative to reduce the incidence of ACL injuries. In addition, in terms of exercise effectiveness, it suggests a 51% reduction in these injuries^{2,20,35,36}.

Based on the review recently published in the journal *Fisioterapia*¹⁶, we proceed to propose, as a continuation of the current research process, an exercise protocol, as well as its dosage in female footballers with DKV, in order to reduce the risk of ACL injuries.

OBJECTIVES AND HYPOTHESES

Main objective

To assess the efficacy of a comprehensive and specific training protocol focused on female players with DKV in preventing ACL injuries.

Specific objectives

1. To investigate the effects of a specific protocol as a preventive method of ACL injuries on the physical performance of female football players.
2. To analyze the injury incidence of ACL among players with DKV in both groups.
3. Check the changes in the neuromuscular control of the knee measured with the "*drop vertical jump test*" (DVJ) in both groups after the corresponding training proposal.
4. To evaluate the biomechanics of landing with jump landing measured with the landing error scoring system (LESS) in participants in both groups.

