5. To analyze the perceived satisfaction rates of the athletes, using the SF-12 questionnaire after the intervention.
6. Know the effective dosage of a specific protocol for the prevention of ACL injuries.

PICO Question

In soccer players with DKV... Does a specific training protocol reduce the risk of ACL injuries compared to the conventional program?

Study hypothesis

A comprehensive and specific 12-week training protocol for the 2023-2024 season will significantly reduce the risk of ACL injuries compared to conventional training for female soccer players with DKV.

METHODOLOGY

Ethical documents and prior registration

This study has the Authorization of the Ethics Committee of the Responsible Research Office of the Miguel Hernández University of Elche for the 2022/2023 academic year and will be registered as a clinical trial in the clinicalTrials platform.

Studio Design

The study is designed as a randomized and controlled, double-blind, unicentric and parallel group clinical trial protocol that will be carried out with the female players of Elche CF and Intercity CF in the province of Alicante. The recommendations of the SPIRIT guide³⁶ have been followed for the realization of this study. Annex I.

Before starting the study, they will be provided with a written informed consent that they must sign to record their intention to participate in it, being able to revoke it at any time and accepting the conditions that will appear in the document (Annex II). They will be randomly assigned to a conventional fitness training program or a specific training protocol for 12 weeks. This study will consist of 3 time measurement points, the first prior to the intervention, the second at the end of the 6-week period of intervention and the last at 4 weeks after its completion. The study schedule and flowchart are in Annex III and IV, respectively.

Participants

The recruited population will be formed by the 44 elite players (22 per team) with a federative record belonging to the first senior team of Elche CF and Intercity CF of the province of Alicante of the national women's football league during the 2023-2024 season, where three weekly training sessions of one hour each are carried out. Prior to the collection of data, permission will be requested from the Club and the coach of both teams to carry out the study at the Martínez Valero Stadium in Elche. In the same way,

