the recruitment will be carried out through a direct contact, as an interview, with the coach, the physiotherapist and the physical trainer of the participating teams.

Inclusion and exclusion criteria

The inclusion criteria will be:

- Football players registered and federated in the corresponding team.
- With an age range between 18 and 35 years.
- Minimum experience of one year playing football.
- With the presence of DKV.

The exclusion criteria will be:

- Previously injured subjects of ACL or other knee ligament injury.
- Subjects with a history of lower extremity injuries that have resulted in surgery during the six months prior to the study.
- Players with chronic illnesses that may affect test results.
- Subjects who practice other sports in the professional field.

Study variables and measurements

To record the number of injuries produced among the players of both groups at the end of the study and the frequency of weekly training, an Excel table will be used. The kinetics and kinematics of the lower extremities will also be analyzed with a motion capture system, surface EMG markers and a force platform. The LESS scoring system (Annex V) and the DVJ task will be used to identify the risk of injury during the jump-landing task and the presence of DKV among the players, respectively. In addition, we will measure their pre- and post-intervention satisfaction rates using the SF-12 questionnaire³⁸. Annex VI.

Sample size

An analysis was performed with Epidat 4.2 software to calculate the sample size required in the present study. A comparison of independent means will be performed and a standardized mean difference of 1, a significance level of 0.05, a 95% CI and a power of 90% will be considered, which determines a total sample size of 44 subjects, 22 in each group. It is necessary to consider an abandonment rate, so we will increase the sample by 10%. Therefore, the total sample size will be 48 women, 24 in each study group. Annex VII.

Randomization and blinding

Teams will be randomly assigned to one of the two groups in a simple manner and will be performed once subject selection has been completed. This assignment will be hidden and will be carried out by a person independent of the study. The randomization method will consist of the toss of a coin assigning "heads" to the intervention group and "tails" to the control group.

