First, qualitative variables will be described with frequencies and percentages. For these variables, hypothesis tests will be performed using the Chi-squared test. On the other hand, quantitative variables will be expressed with median and interquartile range (IQR) or with mean, standard deviation and confidence interval (95% CI). It should be verified that the data follow a normal distribution with the Shapiro Wilk test to test this hypothesis. If it were not met, a nonparametric test such as the Mann-Whitney test would be performed. If, on the other hand, it follows a normal distribution, an ANOVA test will be carried out to contrast the mean difference and assess whether or not the results of the clinical trial have been significant. A level of bilateral statistical significance (limit for judging a result as statistically significant) of $\alpha = 0.05$ shall be established for all hypothesis contrasts. The data will be analyzed with the statistical program SPSS.

Budget estimate

The budget available for this study is limited to material costs, since we have the collaboration of the team of physiotherapists from several clinics in the province of Alicante. Therefore, we will select, from among those who are willing to collaborate, both the evaluating and sports physiotherapists for the study. In addition, they will provide much of the materials needed to conduct the study. If, on the other hand, the collaborating clinics did not have all the necessary material, the cost of more specific devices

such as the mDurance surface EMG (€ 5,500 approx.) and the BMS force platform (€ 3,000 approx.) should be included in the budget.

FUTURE EXPECTATIONS OF THE STUDY

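### The trial's question is whether ACL injuries fall, but its 90% power is for a difference in means and does not carry over to that question

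*Combined protocol and SAP*

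**What the plan says.** **The question.** Under Objectives and Hypotheses, the main objective is "To assess the efficacy of a comprehensive and specific training protocol focused on female players with DKV in preventing ACL injuries". The PICO question asks whether the protocol lowers ACL injury risk. The study hypothesis is that the 12-week programme "will significantly reduce the risk of ACL injuries compared to conventional training for female soccer players with DKV".

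**The sample size.** The Sample size section reads "A comparison of independent means will be performed and a standardized mean difference of 1", with significance level 0.05 and power 90%. This gives 22 per group, raised to 24 for dropout. The section mentions no variable, injury rate, event count or risk reduction. It refers to Annex VII, which is not in the supplied text. No primary outcome is named in the supplied text.

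**Injury data and test.** Study variables and measurements provides a table for "the number of injuries produced among the players of both groups at the end of the study and the frequency of weekly training". For qualitative variables, Statistical analysis states: "For these variables, hypothesis tests will be performed using the Chi-squared test". The two-sided 0.05 level applies to every contrast.

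**Background figures not used in the sizing.** The Introduction says that injury rates "range from 1.1 to 3.1 injuries per 1000 hours of training and from 12.6 to 23.6 injuries per 1000 hours of play" and describes the injuries as "accounting for 16% to 32% of all injuries". Justification for the study says of preventive exercise that "it suggests a 51% reduction in these injuries".

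**The concern.** A standardized mean difference of 1 applies to a continuous measurement. ACL injury is a rare yes/no event per player, and its power depends on how many events occur. The 90% therefore cannot be read as the chance of confirming the stated hypothesis.

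Two consequences follow. If injuries do not differ significantly, the result says almost nothing about whether the programme works, yet it would look like a negative answer from a 90%-powered trial. And because no outcome is ranked first, a favourable movement result could be reported as injury prevention. Expected results already argues that improvements in landing and muscle activation would mean fewer injuries.

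**Working it through.** **1. Reproduce the plan's figure.** Two independent means, SMD 1, two-sided 0.05, power 90%:

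n per arm = 2 × (1.960 + 1.282)² / 1² = 21.01, rounded up to 22.

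The exact t-test power at 22 per arm is 0.8997. The stated 44 is correct for a continuous outcome.

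**2. Power for ACL injury, with no exposure assumption.** Let p be the control risk and 0.49p the intervention risk (the cited 51% reduction). With 22 independent players per arm, exact power is the sum of Bin(i; 22, p) × Bin(j; 22, 0.49p) over all pairs (i, j) for which the uncorrected chi-squared test is significant at two-sided 0.05.

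- 51% reduction: power is 0.897 at p = 0.87 and 0.909 at p = 0.88. So 90% needs about 88% control risk, or 0.88 × 22 ≈ 19 of 22 players.
- At p = 0.50, power is 41%.
- Complete prevention (intervention risk 0): 90% needs p of about 0.28, or about 6 of 22 players (power 0.902).

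**3. Illustration from the protocol's incidence figures.** From the documents: 22 players per team, three one-hour sessions a week, and 16 weeks (12 of intervention plus about a month to the last measurement). Assumed: one 90-minute match a week with 11 on the pitch, and 16% to 32% read as the ACL share of all injuries.

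- Training: 22 × 3 × 16 = 1,056 h. Match: 11 × 1.5 × 16 = 264 h.
- Lower: 0.16 × (1.1 × 1.056 + 12.6 × 0.264) = 0.72 ACL injuries; risk 0.72/22 = 3.3%.
- Upper: 0.32 × (3.1 × 1.056 + 23.6 × 0.264) = 3.04 ACL injuries; risk 3.04/22 = 13.8%.

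| Scenario | Expected control ACL injuries | Power, 51% reduction | Power, complete prevention (upper rate) |
|---|---|---|---|
| Base case | 0.72 to 3.04 | 0.4% to 11% | 36% |
| All 22 play 90 minutes weekly (528 match h) | 1.25 to 5.04 | 2% to 18% | 78% |
| Base case, upper rate doubled | 6.08 | 21% | 89.6% |
| Both upper assumptions | 10.07 | 36% | over 99% |

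Using risk = 1 − exp(−rate) instead lowers the figures: the base-case upper values become 9% and 31%. Fisher's exact test lowers them further, to 5% and 18% at the base-case upper risk.

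**4. Size needed for ACL injury.** Two proportions p₁ = p and p₂ = 0.49p, with mean p̄:

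n = [1.960 √(2p̄(1−p̄)) + 1.282 √(p₁(1−p₁) + p₂(1−p₂))]² / (p₁ − p₂)²

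- p = 0.0326: about 1,798 per arm.
- p = 0.1382: 389 per arm.
- p = 0.4577 (both upper assumptions): 85 per arm.

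The clubs supply 22 each.

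**The case against.** The best defence is that risk here means a measured score. Study variables and measurements and Expected results both use LESS to identify injury risk, and ACL incidence is a separate specific objective. On that reading a comparison of means fits. But the main objective speaks of preventing ACL injuries, and the Sample size section does not tie the calculation to LESS. If LESS was meant, the plan needs to say so.

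Annex VII may name the variable, so its absence from the supplied text cannot be held against the plan. Even so, a named continuous variable would not make a calculation on means cover an injury outcome.

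The chi-squared test on injured yes/no is an inference: the plan records a number of injuries and does not assign a test to it. It is the natural reading of Statistical analysis, but it remains a reading.

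The exposure illustration is soft. Match hours are not in the documents, and 16% to 32% could be read as covering knee injuries more widely, which would lower the ACL figures. Because the hypothesis mentions the 2023-2024 season, a longer window is arguable. With an assumed 40 weeks and the other base-case inputs at the upper rate, power is 27% for a 51% reduction and 97% for complete prevention. The complete-prevention figures therefore depend heavily on follow-up. The 51% conclusion does not change.

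**Conclusion.** The concern holds. The stated 90% power belongs to an unspecified continuous outcome and does not apply to the hypothesis as written. The firmest figure needs no exposure assumption: at 22 per arm, a 51% reduction has 90% power only if control ACL risk is about 88%. Under every exposure tried, including deliberately generous ones, power for that reduction was 36% or less. Adequate power appears only if the programme is assumed to prevent ACL injury completely and the control rate is high.

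All these figures treat players as independent and individually allocated. The plan assigns whole teams by coin toss, one per arm, so even these player-level figures do not strictly hold.

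**What to change.** **Preferred change.**

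- Name one continuous measure already collected, such as total LESS score or a DVJ knee-valgus measure, at one time point, as the single primary outcome. First reconcile the 6-week and 12-week intervention periods in Studio Design.
- Restate the main objective and hypothesis as a change in that risk factor.
- State that SMD 1 and the power figure refer to this outcome only, and give the expected difference and SD behind SMD 1.
- Report ACL injuries by arm as counts and proportions with exact confidence intervals and no efficacy conclusion. Label other contrasts secondary or exploratory.
- Reword Expected results so that a movement change is not said to imply fewer injuries.

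**Restate or qualify the 90%.** The teams hold 44 players before DKV screening, against 48 required. After 10% dropout, 22 × 0.9 ≈ 20 per arm gives 87% at SMD 1. If 70% have DKV (an assumption), 15 per arm gives 75% before dropout and 14 per arm gives 72% after it. The text should also acknowledge the allocation of one team per arm.

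**Alternative.** If ACL injury stays the primary question, size the trial on a stated ACL rate and exposure. At the base-case risks that means hundreds of players per arm and many teams, which two clubs cannot provide.

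**Cost.** The preferred change is rewording of the objective, hypothesis, sample-size text and analysis section. It needs no new measurements, provided the injury table marks which injuries are ACL. A rate per player-hour would need match and training hours to be recorded, which the plan does not provide for. The price is a headline about changing a risk factor instead of preventing ACL injury, and a less favourable power figure.

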First, an invitation will be made to all the players who are part of the teams mentioned above during the 2023-2024 preseason with the aim of starting the intervention during that same season. All respondents will receive a Google survey via WhatsApp. This questionnaire will include questions about the inclusion and exclusion criteria to select the study sample of interest as well as questions about their sports background (position, dominant limb and sports experience); anthropometric measurements (age, height, BMI and weight), which will be provided by the coaches of the selected teams; and aspects related to training (frequency of weekly training and rest period). After completing the survey, three weeks prior to the start of the clinical trial, all players who agree to participate must undergo a final screening to be included in the study. This screening will consist of undergoing a qualitative analysis of the DVJ (Annex VIII), so that, through a simple visual examination, the inclusion of those players who do not present DKV can be ruled out and only those who test positive for DKV can be registered. After selecting the final number of players, a joint talk will be given to both teams to expose the dynamics of the study and the confidentiality of the data. Subsequently, pre-intervention measurements will be carried out by the evaluating physiotherapists to record the initial state of the players. These measures will be: the quantitative analysis of the DVJ, the LESS score, the initial score in the SF-12 scale, the biomechanics of the lower extremities, the muscular activation of the lumbo-pelvic complex and the lower extremity.

During the 12 weeks that the intervention will last, periodic measurements will be made. The last one will take place one month after the end of it. In addition, the players will be asked to refrain from consuming performance stimulants, tobacco or alcohol, non-steroidal anti-inflammatory drugs (NSAIDs) or analgesics 24 hours before each session, as well as strenuous exercise. As a reminder, a WhatsApp will be sent to each athlete the day before each session, indicating the time at which they will be scheduled for training the next day. The appearance of pain during the sessions will not be allowed and, if at any time it appears, the training of the player in question will be stopped immediately and recorded for further analysis.

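### The assessment schedule ties the second visit to the end of a 6-week intervention, while every other statement of this trial's intervention length is 12 weeks

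*Combined protocol and SAP*

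**What the plan says.** The Studio Design section announces three measurement points. The first precedes the intervention. The other two are "the second at the end of the 6-week period of intervention and the last at 4 weeks after its completion". The same paragraph then refers the reader onward: "The study schedule and flowchart are in Annex III and IV, respectively".

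The sentence just before the schedule has players "randomly assigned to a conventional fitness training program or a specific training protocol for 12 weeks". The hypothesis concerns "A comprehensive and specific 12-week training protocol for the 2023-2024 season". The Intervention section states: "During the 12 weeks that the intervention will last, periodic measurements will be made". It continues: "The last one will take place one month after the end of it". It also fixes 3 sessions a week for 12 weeks, 36 in total, in three phases that run to the third month. The section on future expectations presents 12 weeks as longer than existing programmes, and the Limitations list repeats 12 weeks.

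Several outcomes are defined relative to the end of training. Objective 3 looks at the drop vertical jump after the training. Objective 5 assesses satisfaction "using the SF-12 questionnaire after the intervention", and Study variables and measurements asks for SF-12 before and after the intervention. Expected results describes EMG before and after, and scores LESS from the same jump test. Injuries are counted at the end of the study.

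**The concern.** Two adjacent sentences give different lengths for the same intervention, and the second of them sets the visit dates. An intervention of 12 weeks does not end at week 6, so the second and third assessments cannot be dated from the text with certainty.

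What is at stake is which value counts as post-intervention for the jump test, LESS, EMG and SF-12. The Statistical analysis section names no time point, so it does not settle the matter. If sites book visits from the sentence as it stands, outcomes could be measured at a different stage of the programme from the one intended.

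**Working it through.** **Inputs**
- 3 sessions a week, 12 weeks, 36 sessions (Intervention).
- Three assessments; the second at the end of the intervention, described as 6 weeks; the last 4 weeks after completion (Studio Design).
- Last measurement one month after the end of the 12 weeks (Intervention).

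**The plan's own figure**
- Sessions = sessions per week × weeks = 3 × 12 = 36. This reproduces the stated total exactly.
- Read backwards, 36 / 3 = 12 weeks.
- A 6-week intervention would give 3 × 6 = 18 sessions, half the stated total. The session count therefore agrees with 12 weeks and not with 6.

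**Other 6-week figures.** The future-expectations section mentions 6 to 8 weeks, but for earlier programmes, and one reference title mentions six weeks. Neither describes this trial.

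**Assessment weeks under each reading**

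| Reading | First | Second | Last | Sessions done by second visit |
|---|---|---|---|---|
| Literal: the intervention lasts 6 weeks | 0 | 6 | 6 + 4 = 10 | 18 (3 × 6) |
| The 6 is a slip for 12 | 0 | 12 | 12 + 4 = 16 | 36 of 36 |
| Second visit meant as mid-programme | 0 | 6 | 12 + 4 = 16 | 18 of 36 (50%) |

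In the last row, week 16 is approximate, because the Intervention section says one month and not 4 weeks.

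**Comparison with the rest of the text**
- *Literal.* Week 10 is 12 − 10 = 2 weeks before a 12-week programme ends. This contradicts the Intervention section, which places the last measurement after the end.
- *Slip.* This keeps the anchor at the end of the intervention and agrees with every other duration statement.
- *Mid-programme.* This fits the 12-week length and the last visit, but not the words that place the second visit at the end of the intervention. That visit would come before the phase assigned to the third month has begun. The last visit would follow 16 − 6 = 10 weeks later.

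**Injury count.** The last visit is at about week 16 under the slip and mid-programme readings, so the count is the same under both. Under the literal reading it is at week 10. If the study closes at its last visit, which the text does not state, the counting window would be 16 − 10 = 6 weeks shorter.

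**The case against.** The strongest reply is that this is an obvious slip. The preceding sentence says 12 weeks, the Intervention section independently puts the last measurement one month after the 12 weeks, and a careful user would correct the figure unaided. Annexes III and IV may already show the right weeks. Much of this stands: the slip is the likelier explanation, and under it no data are lost. The annexes are not in the text available here. They could settle the dates, but they could not make the Studio Design sentence consistent with its neighbours.

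A second reply is that week 6 was meant as a mid-programme visit, which might inform objective 6: "Know the effective dosage of a specific protocol for the prevention of ACL injuries". That is possible, but the sentence does not say it, and the reading leaves open where the end-of-training value comes from.

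A reader might go further and infer that the trial has no assessment at the end of training, so that its pre/post comparisons are lost. The documents do not support that. No week 12 visit is named by number, but the second visit is tied to the end of the intervention, which is week 12 if the intervention lasts 12 weeks. Even under the mid-programme reading, the undated periodic measurements could include one at the end of training, and the visit a month later is still post-intervention in the plain sense.

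**Conclusion.** The sentence is wrong as written: an internal inconsistency in the operative assessment schedule. The contradiction is certain, but its consequence depends on what was meant.

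- If the 6 is a slip, the effect is on wording only.
- If a mid-programme visit was intended, the second assessment follows 18 of 36 sessions. The jump test, LESS, EMG and SF-12 then lack an end-of-training value, unless the periodic measurements supply one.
- If the sentence is taken literally, the last assessment falls at week 10, and the injury-counting window could be 6 weeks shorter than under the other two readings.

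It would be too strong to say that outcome data are lost, or that the injury count is affected in every case. The sample size calculation uses no intervention length and is untouched. The week numbers assume that training starts at week 0 and runs at 3 sessions a week without a break. No view is taken on which intervention length is right. The point should be corrected before visits are booked, and the correction is probably small.

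**What to change.** Reconcile the 6-week and 12-week statements in Study hypothesis, Studio Design, Intervention, Future expectations and Limitations with each other and with Annexes III and IV. Then:

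1. Correct the Studio Design sentence so that its end of intervention matches the reconciled length.
2. State each assessment as a week counted from the start of the intervention.
3. Say whether the periodic measurements in the Intervention section are these three assessments or additional ones, and give the weeks of any additional ones.
4. Name the assessment that supplies the post-intervention value for the jump test, LESS, EMG and SF-12, and carry that into the Statistical analysis section.

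If the 6 is a slip, the cost is a wording correction and a sentence or two, and no visit moves. If a week 6 visit was intended, the sponsor should say so and state where the end-of-intervention value comes from.
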